### 16.3 Vital signs

#### 16.3.1 Change from baseline to each visit up to Month 6

Summaries of the observed value and change from baseline at each visit will be presented by treatment group, using the windowed times as described in [Table 15](#).

#### 16.3.2 Treatment-emergent marked abnormalities

The number and percentage of subjects with treatment-emergent marked abnormalities will be tabulated by treatment group for each vital sign variable. For blood pressures and heart rate, percentages will be based on the number of subjects at risk for the parameter: those not meeting the criterion at baseline (or with a missing baseline value) and with at least one post-baseline value. For weight, percentages will be based on the number of subjects at risk for this parameter: those with a baseline value and at least one post-baseline value (not later than EOT + 30).

Marked abnormalities are classified as high (H, HH) or low (L, LL) based on values occurring above the higher limit or below the lower limit, respectively. It is possible that, for a given parameter, the same subject is counted as a high marked abnormality for an observed value and as a low marked abnormality for a different observed value. Only the most severe abnormality will be counted (e.g., a subject meeting the “HH” criterion for a specific parameter will not be summarized under “H” for this parameter).

The definitions of marked abnormality used for SBP, DBP, HR, and body weight are presented in [Table 19](#).

**Table 19**      **Marked abnormalities for vital signs**

Variable	Abnormality
SBP (mmHg)	< 90 (L flag) > 140 (H flag) > 180 (HH flag)
DBP (mmHg)	< 60 (L flag) > 90 (H flag) > 120 (HH flag)
HR (bpm)	< 45 (LL flag) < 50 (L flag) > 100 (H flag)
Weight (kg)	decrease from baseline > 10% (L flag) increase from baseline > 10% (H flag)

bpm = beats per minute; DBP = diastolic blood pressure; HR = heart rate; SBP = systolic blood pressure.

## 16.4 12-lead ECGs

12-lead ECG parameters include HR (bpm), PR (ms), QRS (ms), QT (ms), QTcB (ms), QTcF (ms), and any morphological abnormalities as defined by the ECG provider.

### 16.4.1 Change from baseline to each visit up to Month 6

Summaries of the observed value and change from baseline at each visit will be presented by treatment group, using the windowed times as described in [Table 15](#). In addition, summaries of the observed value and change from pre-dose at Month 1 (as recorded in the eCRF) to 2 hours and 4 hours post-dose at Month 1 visit will be presented by treatment group.

### 16.4.2 Treatment-emergent marked abnormalities

The number and percentage of subjects with treatment-emergent marked abnormalities will be tabulated by treatment group for each ECG variable. For a given parameter, percentages will be based on the number of subjects at risk: those not meeting the criterion at baseline (or with a missing baseline value) and with at least one post-baseline value (not later than EOT + 30).

Marked abnormalities are classified as high (H, HH, HHH) or low (L, LL) based on values occurring above the higher limit or below the lower limit, respectively. It is possible that, for a given parameter, the same subject is counted as a high marked abnormality for an observed value and as a low marked abnormality for a different observed value. Only the most severe abnormality will be counted (e.g., a subject meeting the “HH” criterion for a specific parameter will not be summarized under “H” for this parameter).

The definitions of marked abnormality used are presented in [Table 20](#).

**Table 20**      **Marked abnormalities for 12-lead ECGs**

Parameter	Abnormality
HR (bpm)	< 45 (LL flag) < 50 (L flag) > 100 (H flag)
PR (ms)	> 200 (H flag) > 220 (HH flag) < 120 (L flag)
QRS (ms)	> 110 (H flag)
QTcB (ms)	> 450 (H flag) > 480 (HH flag) > 500 (HHH flag) < 340 (L flag)
QTcF (ms)	> 450 (H flag) > 480 (HH flag) > 500 (HHH flag) < 340 (L flag)

ECG = electrocardiogram; HR = heart rate; QTcB = QT corrected according to Bazett's formula; QTcF = QT corrected according to Fridericia's formula.

ECG findings reported by the ECG provider (EG.EGORRES where EG.EGCAT = FINDING) will be listed with a flag indicating ECG examinations with morphological abnormalities as defined by the ECG provider (where EGTEST = Interpretation and EG.EGORRES in [Abnormal ECG, probably non-significant, Abnormal ECG, possibly significant]).

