6.2 Safety endpoints

- Treatment-emergent AEs and SAEs;
- AEs leading to premature discontinuation of study treatment;
- Change from baseline to each visit up to Month 6 in vital signs.
Vital signs include systolic blood pressure (SBP), diastolic blood pressure (DBP), mean arterial pressure (MAP), heart rate (HR), and body weight;
- Treatment-emergent marked^a abnormalities for vital signs up to Month 6;
- Change from baseline to each visit up to Month 6 and from pre-dose to 2 hours and 4 hours post dose at Month 1 in 12-lead ECG variables.
ECG variables include HR, PR, QRS, QT, corrected QT (QTc) and morphological abnormalities as defined by the ECG provider;
- Treatment-emergent marked^a abnormalities for quantitative 12-lead ECG variables up to Month 6;
- Change from baseline to each visit up to Month 6 in laboratory variables [see list in Section 7.2.4.2];
- Treatment-emergent marked^a abnormalities for selected laboratory variables up to Month 6.

^a The selection of marked abnormalities considered for the analyses will be based on standard definitions and described in the SAP.

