7.2.3.3 Weight and height

Height will be measured without shoes at screening.

Body weight will be measured in indoor clothing but without shoes at screening and each visit thereafter.

Body weight and height data will be recorded in the eCRF.

7.2.3.4 *Electrocardiogram assessment*

A standard pre-dose 12-lead ECG will be performed at all scheduled visits. At the Month 1 visit, 2 additional 12-lead ECGs will be performed 2 h and 4 h after study treatment administration.

A re-test may be performed if the result for an ECG is missing or to repeat an abnormal ECG. A re-test does not need to be reported as an unscheduled visit [see Section 7.1.2].

ECGs will be performed with the subject in a fully rested supine position after the subject has been allowed to rest for a minimum of 5 minutes prior to the measurement. The date and exact clock time of ECGs will be entered in the eCRF.

A central ECG vendor (see ECG manual for contact details) will be used for the evaluation of all protocol-mandated ECGs, including re-tests due to ECG abnormalities and ECGs performed at unscheduled visits. The site personnel will electronically transmit the ECGs to the central ECG vendor for central reading.

The following variables will be evaluated by the central ECG vendor: HR (bpm), PR (ms), QRS (ms), QT (ms), QTc according to Bazett's formula (QTcB) (ms), QTcF (ms) and any ECG findings. QTc (ms) will be calculated according to Bazett's and Fridericia's formula ($QTcB = QT/[RR]^{1/2}$ and $QTcF = QT/[RR]^{1/3}$, respectively).

ECG reports will be provided by the central ECG vendor to the investigator/delegate. If specific (pre-defined in the ECG manual) ECG abnormalities are observed, the central ECG vendor will alert the sponsor and the site personnel.

All ECG reports must be reviewed, signed and dated by the investigator or delegate within 10 working days of receipt and filed with the source documentation. The investigator/delegate must indicate on the ECG report whether abnormal values or findings are considered clinically relevant or not. Clinically relevant ECG findings that are known at the time of signing of the ICF must be recorded in the medical history or FD forms of the eCRF. Any clinically relevant ECG abnormalities detected after signing of the ICF must be reported as an AE or SAE as appropriate [see Section 9], and must be followed until the finding returns to normal, is considered stable, or until the change is no longer clinically relevant.

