10.3.5.3 Electrocardiography

Descriptive summary statistics by visit and study treatment will be provided for observed treatment-emergent values and absolute changes from baseline in numeric 12-lead ECG values (HR, PR, QRS, QT, QTcB, and QTcF).

Changes in 12-lead ECG variables (HR, PR, QRS, QT, QTcB, and QTcF) from pre-dose to 2 h and 4 h post dose will be summarized at the Month 1 visit.

Treatment-emergent marked abnormalities for 12-lead ECG variables (HR, PR, QRS, QT, QTcB, and QTcF) will be summarized at all visits and pre/post-dose time points.

In addition, summaries of treatment-emergent morphological ECG abnormalities that were not present before first study treatment intake (using data from the ECG provider) will be provided.

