### 10.4 12-lead ECGs

- Change from baseline to each visit up to Month 6
- Change from pre-dose to 2 hours and 4 hours post-dose at Month 1
- Treatment-emergent marked abnormalities.

12-lead ECG parameters include heart rate (HR; bpm), PR (ms), QRS (ms), QT (ms), QTc according to Bazett's formula (QTcB; ms), QTc according to Fridericia's formula (QTcF; ms), and any morphological abnormalities as defined by the central ECG vendor.

Quantitative results (HR, PR, QRS, QT, QTcB, QTcF) will not be available for hard copy ECGs read by the central ECG vendor (only the interpretation will be available).

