## 20 CHANGES TO ANALYSES PLANNED IN THE STUDY PROTOCOL

### 20.1 Subgroup analyses

The study protocol lists the following subgroups related to pain medications in section 10.3.2.6:

- Background pain medications (none vs monotherapy vs combinations): Monotherapy is defined as the use of pain medications belonging to one single class of pain medication;
- Background opioids (Yes/No);
- Background TCAs (Yes/No);
- Background antiepileptics (Yes/No).

The last two of these were combined into the following subgroup in Section 6 of this SAP:

- Chronic anti-epileptics/anti-depressants (yes, no).

*Rationale for change: the “Background TCAs” subgroup was requested by the FDA during the interaction at the time of protocol design. However, very few subjects are on chronic TCA in this study and a clinical interpretation of such a subgroup analysis would not be possible. On the other hand, the use of chronic anti-epileptics and/or anti-depressants to treat neuropathic pain can be considered as a sign of severity and chronicity of neuropathic pain. Hence, the initial TCA subgroup has been replaced by a broader subgroup including any subject using at least one anti-epileptic or one anti-depressant on at least 21 days during the 4 weeks prior to randomization.*

For the “Background pain medications (none vs monotherapy vs combinations)” subgroup, “monotherapy” was defined as the use of pain medications belonging to one single class of pain medications. In the SAP, “monotherapy” is defined as the use of one single pain medication, i.e., two pain medications from the same class taken for at least 21 days would not qualify as “monotherapy” but as “combination”.

*Rationale for change: at the time of protocol design, it was not expected that some subjects could be on more than one chronic anti-depressant or more than one chronic anti-epileptic. Keeping the original protocol definition would imply that a subject on two chronic anti-epileptics would be allocated to the monotherapy subgroup while a subject taking one anti-epileptic and one NSAID would be allocated to the combination therapy subgroup.*

The word “background” was replaced by “chronic” for all subgroups related to pain medications.

*Rationale for change: the protocol refers to “background pain medications” but omits to specify whether this refers to any background pain medication or chronic pain medication. It makes clinically more sense to assess the subjects with chronic pain medications as a*

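### The SAP replaces the protocol's by-arm summary of new morphological ECG abnormalities with a listing that cannot tell new from pre-existing findings, and does not declare the change

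*SAP*

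**What the plan says.** Protocol 6.2 places morphology within the ECG safety endpoints: "ECG variables include HR, PR, QRS, QT, corrected QT (QTc) and morphological abnormalities as defined by the ECG provider". Protocol 10.3.5.3 states the planned output: "summaries of treatment-emergent morphological ECG abnormalities that were not present before first study treatment intake (using data from the ECG provider) will be provided". Protocol 10.3.5 treats tables and figures as one kind of output and listings as another.

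The SAP (Section 1) says it describes the analyses of all safety endpoints in detail, and Sections 10.4 and 16.4 name morphological abnormalities among the 12-lead ECG parameters. The sentence that specifies an output for them is at the end of Section 16.4.2, below Table 20: "ECG findings reported by the ECG provider (EG.EGORRES where EG.EGCAT = FINDING) will be listed with a flag indicating ECG examinations with morphological abnormalities". The flag is set when the provider's interpretation falls in one of two abnormal categories, one judged probably not significant and the other possibly significant.

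SAP Section 20, on changes from the protocol, has one subsection. It opens "The study protocol lists the following subgroups related to pain medications in section 10.3.2.6" and deals with subgroups throughout.

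**The concern.** The protocol's summary has two features that the SAP's listing lacks. It counts subjects by treatment group, and it is restricted to abnormalities not seen before first intake. The second feature matters in Fabry disease. The disease-history form in Protocol 7.2.1.1 collects arrhythmias, atrial fibrillation, shortened PR interval and ventricular hypertrophy, so some subjects can be expected to enter with abnormal ECGs, although the documents give no rate. A flag on every abnormal reading would then mix existing disease with anything that appears on treatment.

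At stake is a pre-specified comparison of a safety variable between arms. It has been dropped without being declared as a change, so a reader of the study report would not know from the SAP that it had been planned.

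**Working it through.** The protocol commitment was set against each place in the SAP that could satisfy it.

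| Place | What it provides for morphology |
|---|---|
| Protocol 10.3.5.3 | Summary of abnormalities absent before first intake |
| SAP 10 | Treatment-emergent ECGs defined by date only: after the start-of-treatment date, up to EOT + 30 days |
| SAP 16.4.1 | Observed values and changes from baseline; no shift table for the interpretation, although 16.2.1 gives shift tables for categorical laboratory parameters |
| SAP 16.4.2 and Table 20 | By-arm counts with an at-risk denominator, with limits for HR, PR, QRS, QTcB and QTcF only |
| SAP 16.4.2, text after Table 20 | Listing, flagged on the current examination's interpretation |
| SAP 20 | Nothing on ECGs |

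No SAP entry defines a morphology table, and none uses the condition that a finding was absent before first intake.

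**What other by-arm outputs already capture.** Two routes exist.

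1. Limit crossings in Table 20 are tabulated among subjects not meeting the criterion at baseline or with a missing baseline.
2. Under Protocol 7.2.3.4, "Any clinically relevant ECG abnormalities detected after signing of the ICF must be reported as an AE or SAE as appropriate", and SAP 16.1 tabulates adverse events by arm.

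Two kinds of finding fall outside both routes:

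- A new rhythm, block-pattern or repolarisation finding that crosses no Table 20 limit and is not reported as an adverse event. Atrial fibrillation at a rate between 50 and 100 bpm, for example, crosses no heart-rate limit.
- A finding on a hard-copy ECG that is not reported as an adverse event. SAP 10.4 says such ECGs have an interpretation but no quantitative results, so route 1 cannot see them.

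**Size of the listing.** The inputs are the ECG row and footnote f of Protocol Table 5, and the randomized numbers in SAP Section 2 (118; approximately 79 lucerastat and 39 placebo).

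- Before first intake: screening + randomization = 2 (dosing starts on the evening of the randomization visit, Protocol 5.1.2)
- After first intake: Month 1 (pre-dose, 2 h, 4 h) + Months 3, 5 and 6 = 3 + 3 = 6
- Per subject: 2 + 6 = 8
- All subjects: 118 × 8 = 944 scheduled examinations
- Before first intake: 118 × 2 = 236
- After first intake: 118 × 6 = 708, of which lucerastat 79 × 6 = 474 and placebo 39 × 6 = 234

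To rebuild the protocol's summary, a reader would match each flagged later record to that subject's 2 earlier ECGs and then count subjects by arm. The 944 is a count of scheduled examinations, not of flagged or new findings. Missed visits lower it. Unscheduled ECGs, re-tests and the extra end-of-treatment ECG of early discontinuers raise it. Some ECGs in the post-treatment observation period fall after EOT + 30 days and so outside the treatment-emergent window.

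**The case against.** The best counter-reading is SAP Section 14, which says in general terms that data will be listed and summarised, with frequencies and percentages for categorical variables. Since 16.4 names morphology as an ECG parameter and 16.4.1 promises summaries by visit and arm, a by-arm frequency of the provider's interpretation might be thought already planned. Even so, it would count abnormal readings at each visit and not new abnormalities. The specific sentence in 16.4.2, which asks for a listing, also takes precedence over general wording.

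A second point is that Protocol 10.3.5 requires listings to flag records that are not treatment-emergent. Under SAP Section 10 that is a rule about dates. It separates pre-treatment records from later ones but does not separate a persisting abnormality from a new one.

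Third, the remaining gap is narrow. Investigators review and sign every ECG report, the vendor alerts the site and sponsor to pre-defined abnormalities, and relevant findings become adverse events. The thorough QT study was negative up to 4000 mg. This stands as a reason for moderate concern. However, the adverse-event route depends on the site's judgement, whereas the protocol chose the provider's central reading. The QT study gave single doses to healthy subjects, while this trial gives about six months of twice-daily dosing to patients. One of the two serious events in the completed Phase 1 studies was recurrent atrial fibrillation in a subject with Fabry disease (Protocol 1.2.3), although that subject had a history of it.

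Finally, the data are retained and the table could be made later. That is true, but it would then be unplanned.

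**Conclusion.** The concern holds. The protocol plans a summary of new morphological ECG abnormalities, the SAP specifies only a listing with no condition on earlier ECGs, and Section 20 does not report the change. What is lost is the by-arm count of new centrally read findings that cross no Table 20 limit and are not adverse events, together with hard-copy findings that are not adverse events. The up to 944 scheduled examinations (708 after first intake) measure the effort of recovering that count by hand and assume full attendance and the approximate 79/39 split. The documents give neither the rate of new findings nor the number of hard-copy ECGs, so the effect on any safety conclusion cannot be sized. Efficacy estimates and type I error control are not touched. This should be corrected as a departure from a pre-specified safety analysis.

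**What to change.** Add one table to SAP 16.4.2, by treatment group: the number and percentage of subjects with each provider-reported morphological finding that is absent on all ECGs before first intake and present on at least one ECG after the start of treatment, up to EOT + 30 days. Include hard-copy ECGs. A first row for any new finding would help, since rows for single findings may be sparse with about 79 and 39 subjects.

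The denominator should be subjects with a pre-treatment interpretation and at least one post-baseline interpretation, because without an earlier reading a finding cannot be shown to be new. The existing at-risk rule in 16.4.2 keeps subjects with a missing baseline. If that convention is preferred, state it and report how many subjects it affects.

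If only the listing is to be kept, declare and justify the change in Section 20. The cost is one descriptive table from data the vendor already supplies, with no new collection.

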## 17 ANALYSIS OF QUALITY OF LIFE ENDPOINTS

The same approach (ANCOVA) as described in Section 15.4.2 will be used to analyze on the mFAS the changes in the T-score of each of the 8 domains and the change in the T-score of each of the 2 component scores.

The health transition item (question 2: "Compared to one year ago, how would you rate your health in general now?") at baseline and Month 6 will be only listed.

## 18 ANALYSIS OF PHARMACOKINETIC ENDPOINTS

### 18.1 Assumptions

The following assumption is made:

- $C_{max}$ ,  $AUC_{\tau}$ , and  $t_{1/2}$  values are log-normally distributed [Julious 2000].

### 18.2 Calculation of PK endpoints

Plasma PK parameters will be determined by non-compartmental methods using Professional WinNonlin version 8.0 or higher, Pharsight Corporation, Mountain View, CA, USA and calculated on the basis of the actual blood sampling time points.

The measured individual plasma concentrations of lucerastat will be used to directly obtain  $C_{\max}$  and  $t_{\max}$ .

$AUC_{\tau}$  will be calculated according to the linear trapezoidal rule using the measured concentration-time values above the limit of quantification during one dosing interval.

$\lambda_z$  represents the terminal elimination rate constant determined by log-linear regression analysis of the measured plasma concentrations in the terminal elimination phase.

The  $t_{1/2}$  of lucerastat will be calculated as follows:  $t_{1/2} = \ln 2 / \lambda_z$ .

### 18.3 Descriptive analysis of PK endpoints

#### 18.3.1 Listing of plasma concentrations

Plasma concentrations of lucerastat of the PK trough set (including Month 1 PK profile data when applicable) will be listed by subject (displaying the renal function level at screening) and by scheduled time point displaying actual times of blood sampling as well as elapsed actual times. Elapsed actual time in hours will be the number of hours elapsed from date and time of last study treatment intake to actual dates and times of sampling recorded in the (e)CRF.

#### 18.3.2 Plasma concentrations

These concentrations will be summarized on the PK trough set (excluding Month 1 post-dose samples) and on the PK sub-study set by renal function level and overall per time point using number of subjects (n), arithmetic mean, minimum, median, maximum, SD, standard error (SE), and two-sided 95% CI of the mean. Concentrations reported as BLQ will be set to zero. If more than 50% of the values at a given time point are BLQ, no mean (including 95% CI), SD, and SE will be calculated for this time point.

#### 18.3.3 PK parameters

All PK parameters ( $AUC_{\tau}$ ,  $C_{\max}$ ,  $t_{\max}^*$ , and  $t_{1/2}$ ) of lucerastat will be listed by renal function. These parameters will be summarized by renal function level and overall with arithmetic mean, minimum, median, maximum, SD, SE, geometric mean, coefficient of variation between subjects ( $CV_b$ ) in %, and 95% CIs of arithmetic and geometric means [statistical algorithms are detailed in Appendix B].

\* For  $t_{\max}$ , the geometric mean and its 95% CI and CV will not be calculated.

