After single dosing of lucerastat (range: 100–4000 mg) in healthy subjects, peak plasma drug concentrations were attained between 0.5 and 4.0 h, and the apparent terminal elimination half-life ($t_{1/2}$) ranged from 3.6–16.9 h. Following repeated administration of lucerastat (range: 200–1000 mg b.i.d.), peak plasma concentration observed during the dosing interval were attained between 0.5 h and 4.0 h. The PK of lucerastat were proportional for the area under the plasma concentration-time curve (AUC) extrapolated to infinity ($AUC_{0-\infty}$) over the dose range tested after both single and multiple dosing. There was no relevant increase in exposure from Day 1 to Day 7, indicating absence of accumulation over time. The time to reach steady state was approximately 2 days.

Renal clearance of unchanged lucerastat varied from 68–85% of oral clearance and mean renal excretion of unchanged lucerastat per daily dose from 68–85%. No clinically relevant food effect was observed.

The PK results of 1000 mg b.i.d. obtained in subjects with FD were in line with those observed in healthy subjects. The PK profiles of lucerastat were similar in subjects with

mild renal function impairment when compared with healthy subjects. Plasma lucerastat concentrations were higher in subjects with moderate and severe renal function impairment. The $t_{1/2}$ was longer in subjects with moderate (9.6 h) or severe renal function impairment (16.1 h) than in healthy subjects (7.0 h). Overall, this resulted in a 1.6- and 3.2-fold increase in $AUC_{0-\infty}$ of lucerastat in subjects with moderate and severe renal function impairment, respectively, when compared with healthy subjects.

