3.1.3.1 Pharmacokinetic profile sub-study (all sites)

The purpose of the PK sub-study is to further characterize the PK profile of lucerastat. It will be conducted at all sites to determine the PK profile of lucerastat at steady state in a subgroup of approximately 36 subjects with FD with either normal or subnormal renal function (i.e., screening $eGFR \geq 60$ mL/min/1.73 m²) or impaired renal function (i.e., screening $eGFR < 60$ mL/min/1.73 m²). If necessary, blood samples collected for PK may be used for the identification of potential metabolites of lucerastat in this population.

The enrollment in the sub-study will be managed by the Interactive Response Technology (IRT) system and will continue in each of the eGFR subgroups until 18 subjects (12 subjects randomized to lucerastat and 6 randomized to placebo) are enrolled in each subgroup. If the PK sub-study is not fully enrolled when the recruitment target at overall study level (i.e., 108 subjects) is reached, the PK sub-study will not continue recruiting.

Subjects consenting to this sub-study will have a 12-hour PK profile performed at the Month 1 visit. Further details on PK sampling and collection are available in Section 7.2.6.2. PK profile endpoints are defined in Section 6.4.1.

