5.1.2 Study treatment dosing and administration

Subjects will take either lucerastat or matching placebo orally b.i.d.

The starting dose of the study treatment (lucerastat or matching placebo) will be based on the subject's eGFR value (as reported by the central laboratory) at the screening visit as shown in [Table 1](#).

During the study, the dose of the study treatment will be reduced if the subject's eGFR (as reported by the central laboratory during scheduled or unscheduled visits) decreases and crosses the next lower eGFR boundary as shown in [Table 1](#). Upon receipt of the eGFR results from the central laboratory, the investigator/delegate will contact the subject to provide instruction if a dose adjustment is required. The date of the contact with the subjects and the reduced dose will be collected in the eCRF.

Study treatment must be discontinued if one of the study-treatment stopping criteria is met [see Section [5.1.10](#)].

Table 1 eGFR-based study treatment dosing scheme

eGFR (mL/min/1.73 m ²)	Dose regimen (oral)	Number of capsules per dosing
≥ 60	1000 mg b.i.d.	4
≥ 45 and < 60	750 mg b.i.d.	3
≥ 30 and < 45	500 mg b.i.d.	2
≥ 15* and < 30	250 mg b.i.d.	1

* study treatment must be stopped if eGFR < 15 mL/min/1.73m² or in the event that the *acute kidney injury* CTCAE grade 2 or above is met, [see Section [5.1.10](#)].

b.i.d. = twice daily; CTCAE = Common Terminology Criteria for Adverse Events; eGFR = estimated glomerular filtration rate.

Subjects will be instructed to start taking the study treatment on the evening of the randomization visit. Thereafter, the subject should take each study treatment dose in the morning and evening irrespective of food intake. It is preferable that the study treatment be taken each day (morning and evening) at approximately the same time.

Subjects will be instructed not to take study treatment in the morning of study visit days. On the day of the study visits, study treatment must be administered only after the completion of the pre-dose assessments as indicated in [Table 5](#).

If a dose is missed, it should be taken as soon as possible. However, the missed dose should be skipped if it is almost time for the next dose.

To ensure compliance, the study personnel must remind subjects at each visit of the study treatment intake requirements. The reminders must be documented in the hospital chart.

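### SAP 18.3.2 and 18.3.3 tabulate lucerastat concentrations, AUC-tau and Cmax by renal function level and overall without regard to dose, so these rows mix assigned dose with renal function

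*SAP*

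**What the plan says.** SAP 18.3.3 lists AUC-tau, Cmax, tmax and half-life by renal function and then says: "These parameters will be summarized by renal function level and overall". SAP 18.3.2 summarises concentrations, for both the PK trough set and the PK sub-study set, "by renal function level and overall per time point". The concentration listing in SAP 18.3.1 is specified as "displaying the renal function level at screening" together with sampling times; dose is not among the items named. No dose stratum, dose normalisation or apparent clearance appears in SAP 12.2, 18.2 or 18.3, or in Protocol 6.4.1.

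Protocol 5.1.2 (Table 1) assigns 1000 mg b.i.d. at eGFR of 60 or more, 750 mg at 45 to below 60, 500 mg at 30 to below 45, and 250 mg at 15 to below 30. After the start, "the dose of the study treatment will be reduced if" eGFR crosses the next lower boundary. Protocol 3.1.3.1 defines two sub-study levels, screening eGFR of at least 60 and below 60, and recruits until "18 subjects (12 subjects randomized to lucerastat and 6 randomized to placebo) are enrolled in each subgroup".

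SAP section 18 does not define renal function level. SAP 7.5 categorises screening eGFR more finely, with cut points at 45 and 60 among others, but does not link those categories to the PK tables.

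**The concern.** Dose falls as renal function falls, and the two act on exposure in opposite directions. A row defined by renal function alone shows only their net result. Where the row spans two dose bands, it also averages subjects who were given different doses by design. The sub-study fills quotas by renal function and reports by it, so readers will compare the two rows. A ratio of AUC near 1 could mean that renal function has little effect, or that dose reduction has offset a sizeable effect. The planned AUC-tau, Cmax and concentration tables would not show which. The lower row could also look higher or lower than the upper row simply because of how many subjects happened to enrol in each dose band. The printed CV and confidence interval may describe assigned dose differences as if they were variation between subjects.

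**Working it through.** **Inputs**

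- Sub-study size: 12 lucerastat and 6 placebo per level, two levels (Protocol 3.1.3.1).
- Doses by eGFR band (Protocol 5.1.2, Table 1).
- Screening eGFR below 30 is excluded (Protocol 4.4, criterion 2).
- Renal effect, moderate and severe: "Overall, this resulted in a 1.6- and 3.2-fold increase in" AUC extrapolated to infinity, against healthy subjects (Protocol 1.2.3).
- AUC proportional to dose; half-life 9.6 h in moderate impairment and 7.0 h in healthy subjects (Protocol 1.2.3).
- Not in the documents, so assumed: the split of the lower level between 750 and 500 mg, the between-subject CV, and a single 1.6-fold effect across both bands of the lower level.

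**1. The plan's own figure.** 2 × (12 + 6) = 36, which matches the stated sub-study size. Of these, 24 receive lucerastat, 12 per level.

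**2. Doses in each row.** The upper level starts on 1000 mg only. The lower level starts on 750 or 500 mg. Because of the exclusion at 30, nobody starts on 250 mg. That dose, or a reduced dose in the upper level, arises only if eGFR falls on study. For the Month 1 profile that is a short window; it matters more for troughs up to Month 6.

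**3. Raw AUC ratio, lower to upper level.** Relative AUC = (dose / 1000) × fold-increase.

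- All on 750 mg: 0.75 × 1.6 = 1.20
- All on 500 mg: 0.50 × 1.6 = 0.80
- Share w on 750 mg: geometric mean = 1.20^w × 0.80^(1−w)

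| Lucerastat subjects on 750 / 500 mg | Raw ratio | Dose-normalised ratio |
|---|---|---|
| 0 / 12 | 0.80 | 1.6 |
| 3 / 9 | 0.885 | 1.6 |
| 6 / 6 | 0.98 | 1.6 |
| 9 / 3 | 1.084 | 1.6 |
| 12 / 0 | 1.20 | 1.6 |

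With an equal mix and other fold-increases, the raw ratio is fold × √(0.75 × 0.50): 0.61 for 1.0, 0.80 for 1.3 and 1.23 for 2.0.

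**4. Precision of the contrast.** On the log scale, s = √ln(1 + CV²), SE = s × √(2/12), with t on 22 degrees of freedom. For an assumed CV of 20% to 40%, the 95% interval around 0.98 runs from 0.83–1.16 to 0.71–1.36. Around a dose-normalised 1.6 it runs from 1.35–1.89 to 1.15–2.22. The first includes 1 throughout and the second excludes it throughout.

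**5. Effect on the printed CV.** Under a flat 1.6-fold effect, the two bands differ by ln(1.20/0.80) = ln 1.5. Adding the sample variance of that mix to ln(1 + 0.30²) gives a reported CV of 36% (3/9 mix) to 37% (6/6 mix) in place of 30%. If instead AUC at a fixed dose rises 1.33-fold in the upper band and 2.0-fold in the lower, then 0.75 × 1.33 and 0.50 × 2.0 are both about 1.0 and pooling adds nothing. The size of the inflation therefore depends on the assumption.

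**6. Half-life.** Expected ratio 9.6 / 7.0 = 1.37. Under linear PK this does not depend on dose.

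**The case against.** The best defence is that net exposure under the assigned regimen is a legitimate descriptive target. The treatment condition in the estimand tables is the eGFR-adjusted dose. Protocol 2.3 asks only that the PK be documented, and Protocol 3.1.3.1 only that the profile be further characterised. The renal question had its own Phase 1 study of 32 subjects. This stands: nothing in the documents makes the sub-study a test of the Table 1 bands or asks it to isolate a renal effect. It does not fully defend the planned tables, because a row that averages two dose bands describes net exposure in neither of them.

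A reader might infer that the sub-study cannot separate a renal effect from dose at all. The documents do not support that. Half-life is a planned parameter, summarised by renal level, and carries a renal signal, although a 12-hour profile covers only 12 / 9.6 = 1.25 half-lives at the moderate-impairment value. Dose is recorded (SAP 8.1), so the gap is in the planned summaries and not in the data. Nor does every row pool all four doses, as step 2 shows.

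Two further points stand. If renal function level were meant to follow the Table 1 bands, mixing within the lower level would largely disappear; the overall row would still mix doses, and comparisons between levels would still combine dose with renal function. And the protocol states dose-proportionality for AUC only, so normalising Cmax or trough needs an explicit assumption.

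**Conclusion.** The point holds as a gap in interpretability of descriptive PK tables, limited to AUC-tau, Cmax and concentrations. On the protocol's figures, a 1.6-fold AUC effect in the lower renal level would be reported as a raw ratio anywhere from 0.80 to 1.20, with the position in that range set by enrolment mix alone. This rests on three assumptions: that the 1.6-fold figure for moderate impairment applies across the level below 60, that AUC is dose-proportional as stated, and that the two-level definition from the sub-study is the one used in SAP section 18. Inflation of the reported CV is possible, but its size cannot be fixed from the documents. No primary, secondary or safety analysis is affected, and nothing here bears on whether the dosing scheme is right.

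**What to change.** In SAP 18.3.1 to 18.3.3:

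- Keep the raw rows by renal function level and overall.
- Define renal function level: which eGFR cut points, and that the screening value is used.
- Show the dose taken at the sampled visit in the concentration and parameter listings.
- Add summaries of concentrations, AUC-tau and Cmax by actual dose at sampling.
- Add dose-normalised AUC-tau, or apparent clearance as dose / AUC-tau, for the by-level and overall rows.
- Normalise Cmax and trough only with proportionality stated as an assumption.

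Dose, eGFR and concentrations are already collected, so the cost is SAP wording and a few table rows. The drawback is small cells: at most 12 lucerastat subjects are planned in the lower level, spread over at least two doses, and Protocol 3.1.3.1 allows sub-study recruitment to stop before it is full.
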